## 2.2 Study design and conduct

This is a Phase 1, open-label, parallel group, single-center study to investigate the PK, safety, and tolerability profiles of PSL in CYP2C19 genotyped healthy male Japanese study participants.

The study consists of a Screening Period, a Single-dose Period, a Multiple-dose Period, and a Safety Follow up (SFU) Visit. The maximum total duration of the study is 49 days for each study participant, including the Screening Period (up to 28 days), the Single-dose Period (6 days, including Day -1 and PSL single-dose on Day 1 followed by a 4 day washout), the Multiple-dose

Period (9 days, including PSL dosing on Day 6 to 12 and study participants checkout of the center on Day 14), and the SFU Visit (maximum of 8 days after the last dose of PSL on Day 12).

The study participants will be examined for CYP2C19 genotyping (variant alleles: \*2, \*3, and \*17) during the Screening Period and grouped as follows:

- Extensive metabolizers (\*1/\*1),
- Intermediate metabolizers (\*1/\*2, \*1/\*3),
- Poor metabolizers (\*2/\*2, \*2/\*3, \*3/\*3).

Other metabolizers who have the variant allele of \*17 will be excluded from the study. Study participants will not be genotyped, if rescreened.

A total of 39 study participants (13 study participants per CYP2C19 genotype group) will be enrolled. If more than 2 study participants dropout in each group, additional study participants will be recruited at the discretion of the Investigator and Sponsor.

The schedule of activities is provided in Table 2-1.

This document cannot be used to support any marketing authorization application and any extensions or variations thereof.  
REDACTED COPY

**Table 2-1: Schedule of activities**

Study Period	Screening Period (28 days)															SFU Or Withdrawal Visit (maximum of 8 days after the last dose) a	
		Single-dose Period							Multiple-dose Period								
Study Day	-29 to -2	-1	1	2	3	4	5	6	7	8	9	10	11	12	13	14	
Informed consent	X																
Inclusion/exclusion	X		X														
Body weight and height	X																
CYP2C19 genotyping	X																
Exploratory genotyping			X n														
Demographics, habits, lifestyle	X																
Medical/surgical history	X																
Concomitant medication/medical procedures	X	X	X	X	X	X	X	X	X	X	X	X	X	X	X	X	
Physical examination b	X	X														X	
Psychiatric and mental status	X	X	X	X	X	X	X	X	X	X	X	X	X	X	X	X	
C-SSRS	X	X								X				X		X	
Drug screen, ethanol breath test	X	X															
Serology (HBV, HCV, HIV, syphilis)	X																
Clinical laboratory tests	X	X					X							X		X	
Vital signs c	X	X	X	X	X	X	X	X	X	X	X	X	X	X	X	X	

Study Period	Screening Period (28 days)																	SFU Or Withdrawal Visit (maximum of 8 days after the last dose) a
		Single-dose Period					Multiple-dose Period											
12-lead ECG d	X		X	X			X	X	X	X	X	X	X	X	X	X	X	
PSL administration		X e					X f	X g	X g	X g	X h	X i	X i					
PK blood sampling		X j	X j	X j								X k						
PK urine sampling		X l	X l	X l	X l	X l						X m						
Adverse events	X	X	X	X	X	X	X	X	X	X	X	X	X	X	X	X	X	
Stay in study center		X	X	X	X	X	X	X	X	X	X	X	X	X	X	X		

BP=blood pressure; C-SSRS=Columbia-Suicide Severity Rating Scale; CYP2C19=cytochrome P450 family 2 subfamily C; ECG=electrocardiogram; HBV=hepatitis B virus; HCV=hepatitis C virus; HIV=human immunodeficiency virus; PK=pharmacokinetic; PSL=padsevonil; SFU=Safety Follow-up Visit

a The Safety Follow-up Visit will be performed 7 days ( $\pm 1$  day) after the last administration of PSL. Idem for the Withdrawal Visit, if applicable.

b A complete physical examination will be conducted at Screening and SFU. A brief physical examination will be conducted at all other visits, including at discharge.

c On dosing days, vital signs will be performed predose and 3 hours postdose. Blood pressure measurements will be performed in both supine and standing positions for orthostatic measurement at Screening (supine BP after the study participant has been lying down for 5 minutes and then standing BP after 1 minute and 3 minutes) and in a supine position for routine BP measurements at all assessments.

d 12-lead ECG will be performed after a rest of  $\geq 5$  minutes at Screening and at predose, 24 hours postdose, and at the SFU Visit. All ECG recordings will be performed in triplicate but no more than 2 to 3 minutes apart.

e PSL 200mg will be administered in the morning on Day 1 during the Single-dose Period.

f PSL 100mg will be administered in the morning and evening on Day 6 during the Multiple-dose Period.

g PSL 200mg will be administered in the morning and evening from Day 7 to Day 9 during the Multiple-dose Period.

h PSL 200mg and 100mg will be administered in the morning and evening, respectively, on Day 10 during the Multiple-dose Period.

i PSL 100mg will be administered in the morning and evening from Day 11 to Day 12 during the Multiple-dose Period.

j Predose and 0.25, 0.5, 1, 1.5, 2, 3, 4, 6, 8, 12, 24, 36, and 48 hours postdose.

k Predose and 0.25, 0.5, 1, 1.5, 2, 3, 4, 6, 8, and 12 hours after the morning dose.

l Predose and 0 to 12 hours, 12 to 24 hours, 24 to 48 hours, 48 to 72 hours, and 72 to 96 hours postdose.

m 0 to 12 hours after the morning dose.

## 2.3 Determination of sample size

Considering the primary objective and based on UP0057 (with PSL 100mg BID), the inter participant CV of  $AUC_{\tau}$  was estimated to be 39% (PSL). Using an inter-participant CV of 39%, a total sample size of 33 study participants (11 study participants per CYP2C19 genotype group) provides approximately 80% power for concluding that CYP2C19 genotype has no impact on the PK (using acceptance range of 0.5 to 2.0) based on expected ratio of 1.3 in PSL  $AUC_{\tau}$  between CYP2C19 groups at a significance level of  $\alpha=0.05$ .

In order to account for dropouts, the sample size will be increased by 20% (in total 39 study participants).

## 3 DATA ANALYSIS CONSIDERATIONS

### 3.1 General presentation of summaries and analyses

Statistical evaluation will be performed by PAREXEL. The datasets will follow the UCB analysis data model (ADaM) data specifications.

All statistical analysis and generation of tables, figures, participant data listings, and statistical output will be performed using SAS® Version 9.3 or higher (SAS Institute, Cary, NC, USA). The PK noncompartmental analysis (NCA) will be performed using Phoenix WinNonlin®v6.3 (or higher).

Continuous variables will be summarized by treatment period, visit and timepoint (where applicable) including number of participants (n), mean, standard deviation (SD), median, minimum, maximum and confidence intervals (CI) for the mean where stated in the SAP. Geometric coefficient of variation (geoCV), geometric mean and 95% CI for the geometric mean will also be presented in the descriptive statistics for the PK concentration data for PSL and its metabolites. In all outputs the confidence limits will be restricted to the possible values that the variable can take.

When reporting descriptive statistics, the following rules will apply in general (except for PK concentration data):

- N will be an integer
- Mean, SD, and median will use 1 additional decimal place – compared to the original data
- Coefficient of variation (CV) (%) will be presented with one decimal place
- Minimum and maximum will be reported using the same number of decimal places as the original value
- If no participants have data at a given timepoint, then only n=0 will be presented. If n<3, then only the n, minimum and maximum will be presented. If n=3, then only n, minimum, median and maximum will be presented. The other descriptive statistics will be left blank.

When reporting individual values and descriptive statistics for PK concentration data (plasma PK of PSL and PSL metabolites), the following rules will be applied:

- Individual values for PK concentration data will be reported to the same level of precision as the raw data received from the bioanalytical laboratory
- Minimum and maximum of PK concentration data will be reported using the same level of precision as the raw data
- Mean (arithmetic and geometric), median and SD will be reported using 1 additional decimal place or 1 additional significant figure, depending on the reporting format of the original data with a maximum of 3 significant digits
- 95% CI for the geometric mean will use be reported using 1 additional decimal place compared to the value which the confidence interval is constructed
- Geometric CV will be reported as a percentage to 1 decimal place

When reporting individual values and descriptive statistics for PK parameters (plasma PK of PSL and PSL metabolites), the following rules will apply with regard to rounding and precision:

- Individual values for PK parameters will be reported to 3 significant figures
- Descriptive statistics for PK parameters should be rounded to 4 significant figures for the mean, median and SD and to 3 for the others

Categorical variables will be summarized by treatment period, visit and timepoint (where applicable) with frequency counts and percentages.

When reporting relative frequencies or other percentage values, the following rules apply:

- For values where all participants fulfill certain criteria, the percentage value will be displayed as 100
- For values where the absolute frequency is 0, there will be no percentage presented at all.
- All other percentage displays will use one decimal place.

Data listings containing all documented data and all derived data will be generated.

## **3.2 General study level definitions**

### **3.2.1 Relative day**

The relative day of an event will be derived with the date of first dose of investigational medicinal product (IMP), here PSL as reference.

Relative days for an event or measurement occurring before the date of first dose are calculated as follows:

$$\text{Relative Day} = \text{Event Date} - \text{Date of First Dose}$$

The relative day for an event or measurement occurring on the date of first dose is 1. The relative day for an event or measurement occurring after the reference date to the date of the last dose will be calculated as follows:

$$\text{Relative Day} = (\text{Event Date} - \text{Date of Dosing}) + 1$$

For events or measurements occurring after the date of last dose, relative day will be prefixed with '+' in the data listings and will be calculated as follows:

$$\text{Relative Day} = + (\text{Event Date} - \text{Date of Last Dose})$$

There is no relative Day 0. Relative day will not be calculated for partial dates in cases where relative day is shown in a participant data listing. In such cases, relative day should be presented as '--' in the relevant participant data listing.

### **3.2.2 Study periods**

For each participant completing the study, the expected maximum duration of participation will be approximately 49 days with a maximum of 8 days exposure to PSL, and will consist of the following periods:

- Screening Period: Day -29 to Day -2
- Single-dose Period: Day -1 to Day 5
- Multiple-dose Period: Day 6 to Day 14
- SFU or Withdrawal Visit (maximum of 8 days after the last dose)

### **3.3 Definition of Baseline values**

In general, Baseline will be the last non-missing assessment prior to dosing. The definition for each measurement is described below:

- Hematology, serum chemistry, urinalysis: Baseline is defined as Day -1. If Day -1 value is missing the Screening value will be used.
- Vital Signs: Baseline is defined as predose on Day 1. If predose on Day 1 is missing or multiple assessments occur, the last measure prior to dosing will be used.
- ECG: The mean of the last three measurements predose on Day 1 will be taken as Baseline. If there are less than three replicates at Day 1 predose, the mean of the available replicates (predose) will be taken as baseline.

### **3.4 Protocol deviations**

Important protocol deviations (IPDs) are deviations from the protocol which potentially could have a meaningful impact on study conduct or on the primary PK outcome for an individual participant. Furthermore, participants will be excluded from the safety analysis only when there is documented evidence that they received no treatment. The criteria for identifying IPDs and the classification of IPDs will be defined within the protocol deviation specification document.

IPDs will include the following categories:

- Inclusion/exclusion criteria deviations
- Withdrawal criteria
- Prohibited concomitant medication use
- Incorrect treatment or dose

- Procedural non-compliance
- Visit schedule deviations
- Study drug administration deviations (including incorrect treatment received, handling and storage deviations and incorrect dosage received)
- Any vomiting episode(s) (that could impact PK concentrations)
- Missing data
- Other

All IPDs will be reviewed as part of the ongoing data cleaning process and data evaluation. After all data have been verified/coded/entered into a database, a data evaluation meeting (DEM) will be performed.

At least one DEM will be performed at the following time:

- Prior to the final analysis after all data have been verified/coded/entered into the database

Additional DEMs may be conducted as deemed necessary.

The purpose of these DEM reviews will be to review all protocol deviations, define the analysis sets, and check the quality of the data. The reviews will also help decide how to manage problems in the participants' data (e.g. missing values, withdrawals and protocol deviations).

Accepted deviations from scheduled time points will be described in the appropriate documents and included in the Study Master File. After the pre-analysis review, resolution of all issues, and documentation of all decisions (including inclusion into each of the analysis sets) at the final DEM, the database will be locked.

## **3.5 Analysis sets**

### **3.5.1 Enrolled Set**

The Enrolled Set (ES) will consist of all participants who have signed an informed consent form for this study.

### **3.5.2 Safety Set**

The Safety Set (SS) will consist of all enrolled participants who receive at least 1 dose of PSL.

### **3.5.3 Pharmacokinetic Per-Protocol Set**

The Pharmacokinetic Per Protocol Set (PK-PPS) will be a subset of the SS, consisting of those study participants who had no important protocol deviations affecting the PK parameters and for whom a sufficient number of samples are available to determine at least 1 PK parameter.

## **3.6 Treatment assignment and treatment groups**

Unless stated otherwise, listings will be presented by study participant and genotype (Extensive, Intermediate and Poor Metabolizers), and summaries will be presented by treatment period (Single-dose Period and Multiple-dose Period) and genotype.

Study participants who meet all of the inclusion and none of the exclusion criteria will check into the study center on Day -1 (prior to the single dose [SD]). A SD of PSL 200mg will be administered in the morning on Day 1 of the Single-dose Period. During the Multiple-dose Period, PSL will be administered on the following dosage schedule:

- PSL 100mg twice a day (BID) on Day 6
- PSL 200mg BID from Day 7 to Day 9
- PSL 200mg in the morning on Day 10; PSL 100mg in the evening on Day 10
- PSL 100mg BID from Day 11 to Day 12

### **3.7 Center pooling strategy**

The study is planned to be performed at a single center.

### **3.8 Coding dictionaries**

Adverse events and medical history will be coded using the latest available version of the Medical Dictionary for Regulatory Activities (MedDRA®). Medications will be coded according to the World Health Organization Drug Dictionary (WHODD). Medical procedures will not be coded.

### **3.9 Changes to protocol-defined analyses**

- The endpoint to evaluate the safety and tolerability of PSL in healthy male Japanese study participants has been changed from AEs to incidence of TEAEs to align with the summaries of interest
- The following PK parameters of PSL and its metabolites have been included for completeness:  $AUC_{(0-12)}$ ,  $RAUC$ ,  $R_{Cmax}$ , LF and  $R_{m/p}$  based on AUC (for metabolites only).

## **4 STATISTICAL/ANALYTICAL ISSUES**

### **4.1 Adjustments for covariates**

Not applicable.

### **4.2 Handling of dropouts or missing data**

In general, there will be no imputation of missing data unless otherwise stated below. If a Baseline value is missing or not medically implausible, the last value before administration of PSL will serve as Baseline. Missing data for PK results and safety laboratory data will be handled as described in the sections below.

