## 9.2 General statistical considerations

Statistical evaluation will be performed by the Sponsor or designee and supervised by the Early Development Statistics Department of UCB. All statistical analyses will be performed using SAS® Version 9.4 or later (SAS Institute, Cary, NC, USA).

For continuous variables, summary statistics will include number of study participants, mean, median, standard deviation, minimum, and maximum (geometric mean and geometric coefficient of variation [CV] for plasma concentrations and PK parameters). Categorical endpoints will be summarized using number of study participants, frequency, and percentages. Missing data will not be imputed. Individual plasma concentration and PK parameters will be presented using 3 significant digits.

If not otherwise stated, Baseline will be the last assessment prior to dosing. Measurement of specific Baseline values will be described in the SAP.

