### **9.7 Handling of dropouts or missing data**

The methods for handling dropouts will be described in the SAP. Data of study participants prematurely terminating the study will be used to the maximum possible extent. No procedures for replacing missing data are intended. If a Baseline value is missing or not reliable, the last value before administration of study medication will serve as Baseline.

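### SAP 4.2 reverses the trigger for replacing a doubtful Baseline value, and deleting the stray "not" would not by itself repair the rule

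*SAP*

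**What the plan says.** The replacement rule in SAP 4.2 reads: "If a Baseline value is missing or not medically implausible, the last value before administration of PSL will serve as Baseline". Protocol 9.7 has the parallel sentence with a different second condition: "If a Baseline value is missing or not reliable, the last value before administration of study medication will serve as Baseline".

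The general definition of Baseline is nearly the same in both documents. SAP 3.3 has "In general, Baseline will be the last non-missing assessment prior to dosing", and protocol 9.2 has "If not otherwise stated, Baseline will be the last assessment prior to dosing". SAP 3.3 then gives a rule for each type of measurement:

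- Laboratory (Baseline is Day -1): "If Day -1 value is missing the Screening value will be used".
- Vital signs (Baseline is pre-dose on Day 1): "If predose on Day 1 is missing or multiple assessments occur, the last measure prior to dosing will be used".
- ECG (Baseline is the mean of the last three Day 1 pre-dose recordings): "If there are less than three replicates at Day 1 predose, the mean of the available replicates (predose) will be taken as baseline".

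SAP 4.3 makes the latest pre-dose repeat at the Baseline visit the Baseline. SAP 1 lets the protocol govern only where the SAP does not specify otherwise. SAP 3.9, which lists changes to the protocol's analyses, does not mention this rule.

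**The concern.** The two replacement sentences should describe one rule, but their second conditions point in opposite directions. Because the SAP does specify the matter, its wording takes precedence, and a programmer who follows it literally keeps an implausible Baseline.

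The obvious repair, striking *not*, leaves a second difficulty. The rule sends the analyst to the last value before dosing, which is how Baseline is already defined in general.

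Baseline is the reference for change-from-Baseline summaries of laboratory, vital-sign and ECG data, for laboratory shift tables, for the QTcF change categories and for the change component of the vital-sign criteria in Table 10-2. One Baseline value is reused for every later time point of that participant.

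**Working it through.** The plan gives no figure to reproduce, so the check is mainly one of logic.

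**Step 1: the trigger.** An implausible value is taken here to be one that the protocol would call unreliable.

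| State of the Baseline value | Protocol 9.7 | SAP 4.2 as written | SAP 4.2 with *not* deleted |
|---|---|---|---|
| Missing | replace | replace | replace |
| Present, plausible | keep | replace, normally with the same value | keep |
| Present, implausible | replace | **keep** | replace, normally with **the same value** |

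The missing row works in every version. The defect lies in the last row.

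**Step 2: the replacement value, by type of measurement.**

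- *Vital signs.* Baseline is the Day 1 pre-dose reading. If it is implausible and was not repeated, it is itself the last value before dosing, so the repaired rule returns it. Screening and Day -1 readings exist in the schedule, but the rule does not reach them.
- *Laboratory.* Baseline is the Day -1 sample. Unless an unscheduled sample was taken later but before dosing, that sample is also the last pre-dose value. The Screening result is available, but SAP 3.3 opens it only when Day -1 is missing.
- *ECG.* Baseline is a mean, and a single last value is not the same quantity. Here the difficulty is a mismatch: SAP 4.2, applied literally to a plausible ECG Baseline, conflicts with the triplicate mean required by SAP 3.3 and 4.2.3. Nothing removes an implausible replicate from the mean.

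None of the three rules in SAP 3.3 is triggered by implausibility. SAP 4.3 takes the latest repeat whether or not it is plausible. Protocol 9.7 has the right trigger but the same target, so reverting to it would not complete the repair.

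**Step 3: what a wrong Baseline does to the outputs.**

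- *Change from Baseline.* An error of size e in Baseline shifts every later change for that participant by -e.
- *Vital-sign flags.* Footnote a of Table 10-2 requires both the absolute and the change condition. Suppose the true Baseline systolic pressure is 120, it is recorded as 100, and later readings are 120. The apparent change is 120 - 100 = +20, but 120 is not above 140, so there is no flag. Now take a later reading of 141, which does cross the absolute limit; it is flagged only if Baseline is at most 141 - 20 = 121. A true 120 recorded as 140 turns a change of +21 into +1 and loses the flag. A true 140 recorded as 120 turns +1 into +21 and creates one.
- *QTcF change categories (30 and 60 msec).* No absolute limit applies. An error e in one of three replicates shifts the Baseline mean by e/3, so a shift of 30 msec from a single replicate needs an error of 3 x 30 = 90 msec. Smaller shifts matter only near a boundary.
- *Weight of one participant.* With 13 planned per genotype group, 1/13 = 7.7%.

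**The case against.** The strongest reply is that this is a slip of wording whose intent can be recovered from protocol 9.7, and that other steps in the plan would catch most cases. A suspect reading that is retaken before dosing is superseded under SAP 4.3. SAP 3.4 requires a data evaluation meeting before lock to check data quality and decide how to handle data problems. Both safeguards are real, but neither is a rule on plausibility. The SAP contains no criterion for implausibility, and the latest repeat is used even if it is the implausible one.

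Three stronger readings are tempting, and the documents do not support them:

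- A reader might infer that one bad Baseline would flag or mask a participant at every later time point. The cells of Table 10-2 say and/or, but footnote a requires both conditions. A Baseline error alone therefore cannot create a flag, and it can hide one only at a reading outside the absolute limit.
- A reader might infer that the rule is circular throughout. It is not: the missing-value branch works, the ECG Baseline is a mean, and a later unscheduled pre-dose laboratory sample would be a different value. Circularity holds mainly for vital-sign and laboratory values that are present and unrepeated.
- A reader might infer that an implausible Baseline is certain to be analysed, or that the main results are at risk. Repeats and the data evaluation meeting make the first uncertain. The second is wrong, because the primary PK parameters use no Baseline.

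**Conclusion.** The point stands as a minor correction. SAP 4.2 states the opposite of protocol 9.7 on when a present Baseline value is replaced, and the change is not declared in SAP 3.9. Removing *not* is necessary but insufficient for an unrepeated vital-sign or laboratory value.

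The consequences are limited to descriptive safety summaries, and the documents give no basis for estimating how often an implausible, unrepeated Baseline would occur; it is assumed to be rare. The 7.7% assumes the planned 13 per group and a single affected participant. The conclusion also assumes that the sponsor meant what protocol 9.7 says, and that the footnote to Table 10-2 governs over the and/or in its cells.

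**What to change.** Replace the sentence in SAP 4.2 with wording such as:

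> If a Baseline value is missing or judged medically implausible, Baseline is the most recent non-missing, medically plausible value obtained before the first PSL dose. For ECG, Baseline is the mean of the plausible pre-dose replicates or, if there are none, of the most recent earlier plausible set. Implausibility is decided and documented at the data evaluation meeting before database lock.

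Then align the measurement-specific rules in SAP 3.3, which have no plausibility trigger, and the repeat rule in SAP 4.3, which takes the latest pre-dose value regardless of plausibility.

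The cost is one reworded rule and two conforming edits. No extra data are needed: the schedule already provides Screening and Day -1 vital signs, and Screening laboratory tests and ECG, as earlier values.
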